**VERSION DATE: February 7, 2019** 

### **1.0 Purpose of the Study:**

Approximately 10-15% of the 9 million adults with severe mental illnesses (SMI) are employed, which is associated with reduced psychological distress. However, the employment rate increases to  $\sim 30\%$  in adults with SMI enrolled in Supported Employment (SE) (i.e., the gold standard for vocational training). A recent model of SE shows that active job-seeking behavior (e.g., completing job interviews) is an essential treatment target for employment, and finding a job is moderated by self-efficacy and anxiety about interviewing. Moreover, these targets are underdeveloped as adults with SMI have poor interviewing skills and want training to alleviate their fears and poor self-efficacy related to interviewing7-14. Currently, SE relies on role-play training led by "Employment Specialist" counselors to enhance interview skills, but SE clients reported that this method did not improve their skills. In response, NIMH funded the development of Virtual Reality Job Interview Training (VR) and evaluation of VR efficacy in a series of randomized controlled trials (RCTs, R44 MH080496). The results suggest that VR hit the targets by improving interview skills and self-efficacy in several cohorts with SMI  and demonstrated efficacy by increasing the likelihood of getting job offers. Of note, the integration of new technologies into SE is a top research priority for SE developers. Thus, VR is an ideal intervention to evaluate as an effective enhancement to SE. Thus, there are a series of critical next steps to test if VR is effective at improving vocational outcomes for SE clients with SMI. A first step will test if replacing SE interview training with VR enhances person-level (e.g., higher employment rate) and b) system-level (e.g., staff efficiency and costeffectiveness) SE outcomes. A second step will evaluate the initial implementation of VR within SE, while a third step will evaluate potential mechanisms for enhanced SE outcomes.

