### **11.0 Potential Benefits to Participants:**

Participants randomized to the VR training group may experience an increased likelihood of receiving a job offer. This effect was observed in five efficacy studies. Across those 5 efficacy studies, approximately 50% of

VR trainees received a job offer compared to approximately 25% of study participants who received services-asusual. Participants randomized to the control group are not likely to receive a direct benefit from participating in this study.

Participants completing the focus groups or semi-structured interviews for the implementation study are not likely to receive a direct benefit from participating in this study.

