Data Analysis Plan for Aims 1 & 2. In this intent-to-treat study, we will collect data on 160 subjects. The biostatistician will monitor the data for distribution normality and transform abnormally distributed variables if needed. Correction for Multiple Comparisons: To minimize spurious findings, we will adjust the 3 primary tests using a false discovery rate at 0.05 (see below). Covariates: Although randomization should protect against group differences, we will covary for any between-group differences that are observed regarding demographic, cognitive, clinical and vocational history, booster sessions, and the number of completed interviews. Missing Data: We will follow the intent-to-treat principle and in longitudinal analyses we will use multiple imputation models to analyze the data in the presence of missing data. Data processing and cleaning will occur during the study, including checking for missing data and inconsistencies. All videos will be stored on the project's secure server. A Data Safety and Monitoring Board will monitor for adverse events (see 15.0 below).

**Hypothesis 1:** IPS+VR trainees will have higher employment rates than IPS Only by T3. **To test H1**, we will use multiple logistic regression and a Wald Chi-square test of the coefficient to its standard error, to compare the adjusted employment proportions in the two conditions (attained a job=1 vs. failed to attain a job or censored with a job=0, between T1 and T3). We calculated power using simulation in R, correcting for small samples and multiple testing with false discovery rate for the 4 primary tests (our power analysis is conservative, relying on Bonferroni corrections for all tests). Accounting for 10% missing, our trial that recruits 80 subjects in each arm has 80% power for a two-sided 0.05/4=.0125 level test when the OR = 3.2, with IPS+VR effectively doubling the

rate from 25% to 53% employment. Based on our earlier study where we found an OR of 8.7, or effectively tripling the employment rate from 25% to 75%, and a power of 0.99 at this magnitude of effect, we feel confident that we will have sufficient power in this study.

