**Hypothesis 2:** IPS+VR trainees will have greater improvement in *job interview skills* than IPS Only by T2. **To test H2**, we will conduct a repeated measures analysis of variance (RM-ANOVA) with pre and post interview scores as the repeated measures and treatment group as the fixed factor. Based on our pilot data, we expect r=.7 between T1 and T2 scores, and an effect size of d=.67 between pre and post interview role-play scores using VR. Assuming a small-to-moderate effect within IPS Only (e.g., d=.25), our best power estimate assumes a medium effect size contrasting IPS Only with IPS+VR (d=.67-.25=.42). This effect size and correlation imply an expected 6.9% reduction in within subject error for the treatment–x-time effect. Thus, 80 subjects at .0125 level will yield 82% power to detect this effect. For the ANOVA model, 160 subjects will be sufficient to detect a reduction of within subject error of 4.7% with 80% power. Assuming a full sample effect size of d=.46 (.67+.25)/2), this reduction in error corresponds to an effect size of d=.62 for the IPS+VR group and d=.30 in the IPS only group (a difference of d=.32).

**Hypothesis 3:** IPS+VR will get jobs sooner than IPS only by T3. **To test H3**, we will use a Cox proportional (or non-proportional) hazards regression model to assess the adjusted hazard rate on time-to-employment for IPS+VR vs. IPS Only, adjusting for potential covariates (e.g., completed training trials). For a power analysis for **H3**, we assume a constant hazard rate for the distribution of time-to-employment in both groups. We also assume that a proportion of 0.20 of the subjects in the IPS Only group will find a job by T3 (that is, a hazard rate of 0.0085 for IPS Only). This analysis is estimated based on limited pilot data and log-rank power tables. Thus, 160 subjects provide 80% power for a 0.0125-level test comparing time-to-employment in the two arms to detect a hazard rate of 2.0 for IPS+VR vs. IPS Only.

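### H1 and H3 plan the same event, a job by T3, with different IPS Only rates and target effects; H1's odds ratio does not match its percentages, and H3's 80% power does not follow from its own inputs

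*Combined protocol and SAP*

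**What the plan says.** All the planning figures are in Section 14.0, Data Analysis Plan for Aims 1 & 2.

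- **H1 (job attained between T1 and T3).** The test is specified as follows: "we will use multiple logistic regression and a Wald Chi-square test of the coefficient to its standard error". The sample is given as "Accounting for 10% missing, our trial that recruits 80 subjects in each arm", and the claim is "80% power for a two-sided 0.05/4=.0125 level test when the OR = 3.2", described as raising the "rate from 25% to 53% employment". The paragraph closes by citing an earlier study with "an OR of 8.7, or effectively tripling the employment rate from 25% to 75%, and a power of 0.99 at this magnitude of effect", and takes from it that power will be sufficient.
- **H3 (time to employment by T3).** With a constant hazard in each arm, it assumes that "a proportion of 0.20 of the subjects in the IPS Only group will find a job by T3" (hazard 0.0085). It states that 160 subjects give 80% power at the .0125 level to detect a hazard ratio of 2.0.
- **Section 11.0** summarises five efficacy studies: about 50% of "VR trainees received a job offer compared to approximately 25% of study participants" on services as usual.

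**The concern.** H1 and H3 look at one event through two tests. Someone who has found a job by T3 is a success for H1 and an event for H3, so H3's cumulative incidence at T3 is H1's proportion. One trial cannot be planned on both 25% and 20% for the same IPS Only rate. The target effects also differ once they are put on a common scale. Two paragraphs that each report 80% power at the same level and sample size look mutually supporting, but they describe different scenarios.

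At stake is what a reader may conclude about sensitivity. If the effect H3 treats as worth detecting were the true one, H1 would usually miss it, and a non-significant H1 could then be over-read as evidence of no effect. The closing reassurance adds to this, because it rests on the large effect of a single earlier study.

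**Working it through.** **Inputs.** H1: 80 per arm less 10% = 72 per arm analysed; two-sided .0125 (z = 2.498); Wald test of the log odds ratio; 25%; OR 3.2; 53%. H3: 20%, hazard ratio (HR) 2.0, 160 subjects, .0125. Section 11.0: about 25% and 50%. H1 powers below are exact enumerations of the two-binomial Wald test without covariates, unless stated otherwise.

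**1. H1's own figure.** The odds at 25% are 1/3. Multiplying by 3.2 gives 1.067, so p = 1.067/2.067 = 51.6%. Power at 25% versus 51.6% with 72 per arm is 79.7%, so the stated 80% reproduces.

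**2. Odds ratio against percentages.** The odds at 53% are .53/.47 = 1.128, and 1.128/(1/3) = 3.38. Power at 25% versus 53% is 84.2% by the uncorrected Wald test. With a small-sample correction it is 80.0% (continuity-corrected chi-square) or 80.2% (Fisher). The stated 80% is therefore compatible with either pair, depending on the test that was simulated.

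**3. H3's rates.** Reading 0.0085 as weekly over 26 weeks: 1 − exp(−0.221) = 19.8%, which agrees with 20%. At HR 2.0 the IPS+VR proportion is 1 − 0.80² = 36%.

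**4. H1's target on H3's scale.** HR = ln(.47)/ln(.75) = 2.62, against 2.0.

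**5. H1 power in each scenario.**

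| IPS Only vs IPS+VR | OR | 72 per arm | 80 per arm |
|---|---|---|---|
| 25% vs 51.6% (H1, by OR) | 3.2 | 79.7% | 83.9% |
| 25% vs 53% (H1, by rates) | 3.38 | 84.2% | 88.0% |
| 20% vs 44.4% (H3 control rate, H1 OR) | 3.2 | 74.6% | 79.5% |
| 20% vs 36% (H3 target) | 2.25 | 35.0% | 39.2% |
| 25% vs 50% (Section 11.0, job offers) | 3.0 | 73.7% | 78.3% |

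**6. H3's own figure.** Expected events = 160 × (.20 + .36)/2 = 44.8.
- Schoenfeld: Φ(√44.8 × ln 2/2 − 2.498) = Φ(2.320 − 2.498) = 43%.
- Freedman: Φ(√44.8 × (2 − 1)/(2 + 1) − 2.498) = Φ(2.231 − 2.498) = 39%.
- Events needed for 80%: 4(2.498 + 0.842)²/(ln 2)² = 93 (Schoenfeld), or 9(2.498 + 0.842)² = 101 (Freedman).
- Even at two-sided .05, Schoenfeld gives 64%.

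The stated 80% does not reproduce. At H1's rates instead (160 × .39 = 62.4 events, HR 2.62), Schoenfeld gives about 91%. H3's power therefore depends heavily on which scenario is adopted.

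**7. The reassurance.** OR 8.7 from 25% gives odds of 2.9, that is 74.4%, which matches the stated 75%. Power at 25% versus 75% exceeds 99%, so the stated 0.99 is not too high.

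**The case against.** The strongest reply is that an odds ratio of 3.2 and a hazard ratio of 2.0 are each written as the effect detectable by its own test. Neither is a forecast, so 53% and 36% are not two predictions of one number. That stands. It means the 35% is H1's power at H3's target effect, and no more than that. A reader might infer that H1's true power lies somewhere between 35% and 80%, but the documents do not support this. If only the control rate moves to 20% and the odds ratio stays at 3.2, H1's power falls about five points, to 74.6%.

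Four further points have weight:
- The odds-ratio mismatch may be rounding. A control rate of about 26% with 53% gives 3.2, and a small-sample correction brings 25% versus 53% to 80%.
- A reader might take Section 11.0 to contradict H1. It does not. Its figures are approximate, count job offers, and compare with services as usual. Joining its 50% to the rate of about 30% for supported employment in Section 1.0 would create a scenario that the plan states nowhere.
- The .0125 level is a deliberately conservative Bonferroni level, while the planned correction controls the false discovery rate. The powers above are at the cautious end.
- Section 3.0 plans to recruit 180. With 10% lost, about 81 per arm would be analysed, and 25% versus 50% would give 79%. H1's own text, however, recruits 80 per arm and allows for 10% missing.

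None of this reconciles 25% with 20%, and none of it restores H3's 80%.

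**Conclusion.** The point holds in a limited form. H1 and H3 use different IPS Only rates (25% and 20%) and different target effects (hazard ratio about 2.6 and 2.0) for one event. H1's 80% is sound on its own inputs, with a small mismatch between an odds ratio of 3.2 and 53%. The larger numerical error is H3's: its inputs give 39% to 43% power, not 80%. The 0.99 is arithmetically sound; its weakness is that it rests on one earlier study.

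These conclusions assume that both hypotheses count the same event, that T1 to T3 is 26 weeks (this affects only the reading of 0.0085), that hazards are constant as H3 states, and that there is no covariate adjustment. The H3 powers also assume no censoring before T3. Earlier loss would lower them: with 144 subjects they are 35% to 38%.

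**What to change.** - Adopt one IPS Only rate and one target effect for both hypotheses, and express it as proportions, odds ratio and hazard ratio together.
- Make H1's odds ratio and percentages agree, using whichever pair the simulation actually used: 25% to 51.6% for 3.2, or 25% to 53% for 3.4. State the small-sample correction.
- Recompute and restate both powers. If H3's 20% and 36% are kept, report about 35% for H1 (39% with 80 per arm) and 39% to 43% for H3.
- Keep the figure from the earlier study only with its source made plain. Beside it, give H1's power at 25% versus 50% (about 74% with 72 per arm), labelled as the approximate job-offer rates against services as usual in Section 11.0.

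The cost is a short recalculation and revised wording in Section 14.0. Some stated powers become less favourable. Enrolment does not change.

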**D. 4. Randomization for Thresholds' Clients.** After the video-recorded pre-training role-play interviews are completed, participants will be randomized into the intervention group or the wait list control group. Block randomization tables will be created prior to the study based on computer generated blocks of six. Blocks of six will ensure nearly equal groups. Sealed envelopes containing the randomization by sequential subject entry number will be created and stored, and then opened when a participant has completed pre-randomization procedures.

**D. 5. Visits 4-9, Virtual Reality Job Interview Training Delivery.** Participants randomized to the VR training group will complete their VR training at local Thresholds location (see Appendix A), or if requested by the member (at their home). After members have completed their VR-JIT orientation and have demonstrated independence at using VR-JIT with minimal support from staff and completed at least 10 virtual interviews in lab, then study team will support the member to use VR-JIT at home if home use is requested by the member. To provide this support, the research team will show the member how to access the tool in the lab. Moreover, the member will be instructed to call the research team so that the research team can walk the member through accessing the tool once they are at home. In addition, the research team will provide the member with a instructional document so that they can access the tool from home.

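### H2 is tested as pre-post change; adjusting for the baseline role-play score would estimate the same effect with about 7 points more power, at no cost

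*Combined protocol and SAP*

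**What the plan says.** Section 14.0 (Data Analysis Plan for Aims 1 & 2, Hypothesis 2) states that "we will conduct a repeated measures analysis of variance (RM-ANOVA) with pre and post interview scores as the repeated measures", with treatment group as the fixed factor. The power paragraph says "we expect r=.7 between T1 and T2 scores" and takes a between-arm difference of .42 SD (.67 minus .25). It says these values "imply an expected 6.9% reduction in within subject error" for the treatment-by-time effect and concludes: "Thus, 80 subjects at .0125 level will yield 82% power to detect this effect".

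No baseline-adjusted analysis is named for H2. The general covariate rule at the start of the data analysis plan adjusts only for characteristics on which the arms are seen to differ, and does not list the baseline role-play score. Hypothesis 4 does have an ANCOVA, on T3 distress given T1 distress.

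Section 4.0, D.4 places randomization after the pre-training role-plays, so the T1 score is a true pre-randomization covariate.

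**The concern.** A change-score analysis subtracts the whole baseline score from the post-test score. When the correlation is below 1 and the SDs are equal, that subtracts too much and adds noise. ANCOVA estimates the slope from the data and so removes only what the baseline predicts. In a randomized trial with a pre-randomization baseline, both target the same treatment effect, and the baseline score is already collected on everyone randomized.

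H2 is powered at the .0125 level that the plan uses for its primary tests. An arm effect on role-play scores is also the first step of the H6 mediation analysis. Unused precision here could cost a finding that the trial's data would otherwise support.

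**Working it through.** **Inputs (Section 14.0 unless noted)**
- Difference in change: d=.42, in raw SD units.
- T1–T2 correlation: r=.7. Equal SDs at T1 and T2 are assumed.
- Level: .0125. H1 gives the sidedness: "80% power for a two-sided 0.05/4=.0125 level test".
- Arm size: "our trial that recruits 80 subjects in each arm", as stated under H1. Allocation is 1:1 (Section 4.0, D.4: "Blocks of six will ensure nearly equal groups").
- Missing data: 10%, stated under H1. It is not mentioned for H2.

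**Step 1: error variance.** With unit SDs, the variance of T2 − b·T1 is 1 − 2br + b².
- Change (b=1): 1 − 1.4 + 1 = .60, SD .775.
- ANCOVA (b=r=.7): 1 − .98 + .49 = .51, SD .714.
- Ratio: .60/.51 = 1.18. The inverse is (1+r)/2 = .85.

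**Step 2: reproduce the plan's figures.**
- f² = (d/SD)²/4 = (.42/.775)²/4 = .0735, so partial eta-squared = .0735/1.0735 = 6.85%. The plan says 6.9%.
- Noncentrality = d/(SD·√(2/n)). With 80 per arm, .42/(.775 × .158) = 3.43. Power is 81.5% by noncentral t and 82.4% by normal approximation. The plan says 82%.
- If the 80 subjects were the total (40 per arm), power would be about 45% (47% by normal approximation). The stated 82% therefore means 80 per arm, analysed as change, with no loss.

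**Step 3: the same calculation with ANCOVA** (SD .714, one fewer degree of freedom). With 80 per arm the noncentrality is .42/(.714 × .158) = 3.72. Results by noncentral t, two-sided .0125:

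| Analysed per arm | RM-ANOVA (change) | ANCOVA | Gain (points) |
|---|---|---|---|
| 72 (80 less 10%) | 76.4% | 83.9% | 7.5 |
| 80 | 81.5% | 88.2% | 6.7 |
| 90 (the 180 in Section 3.0, no loss) | 86.6% | 92.1% | 5.5 |

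A simulation of 20,000 trials with 80 per arm gave 81.6% and 88.0%.

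**Step 4: other ways to state the size.**
- Difference detectable with 80% power: .413 against .381 SD with 80 per arm; .436 against .402 with 72.
- ANCOVA reaches the power of 80 per arm on change with .85 × 80 = 68 per arm.

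**Step 5: sensitivity to r** (80 per arm, .0125). At r=.5, 55.3% against 70.5%. At r=.6, 67.1% against 78.5%. At r=.8 the gain is only 1.9 points.

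**The case against.** The planned test is valid. H2 is worded as greater improvement, and RM-ANOVA tests that directly. It is unbiased under randomization, and its stated power reproduces. All of this stands, so the point concerns efficiency only.

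The drop below 80% depends on the base and the threshold:
- **Base.** Section 3.0 speaks of recruiting 180. Taking 10% off leaves 81 per arm, where power is 82.1% for change and 88.7% for ANCOVA, so both exceed 80%. The 72 per arm follows the power section's own 80 recruited per arm. The documents conflict, and the shortfall holds only on the smaller base.
- **Threshold.** The planned correction is a false discovery rate at .05, and the plan itself calls Bonferroni conservative. With 80 per arm the gain is 6.7 points at .0125, 4.9 at .025 and 3.3 at .05. With 72 per arm, RM-ANOVA reaches 83.7% at .025. This also stands: about 7 points applies to the level at which the plan states its power.

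A correlation of .7 is not itself a reason to prefer ANCOVA. With equal SDs it is more precise at any r below 1, and a higher r narrows the gap. Since r rests on pilot data, the gain could be smaller or larger than stated. Section 4.0 allows the follow-up role-play by video or telephone, which might lower r.

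Change scores also use the baseline, so better handling of chance imbalance is not a separate benefit beyond the precision already counted. On H6, the plan does not say which model its first step uses and simulated its power separately, so the carry-over there is plausible but not quantified.

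The H2 paragraph's second power statement (160 subjects, 4.7%, 80% power) is a separate matter: 4.7% gives about 61% power at .0125 and 79.7% at .05. It does not affect this comparison.

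**Conclusion.** The concern holds. On the plan's own inputs, the two-time-point RM-ANOVA gives up 6.7 points of power with 80 per arm and 7.5 points with 72, compared with an ANCOVA on a score already collected before randomization. Equivalently, it needs about 18% more participants for the same precision.

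The figures assume equal SDs at T1 and T2, a common within-arm correlation of .7, d=.42, two-sided .0125, and 80 subjects read as 80 per arm. Across the scenarios examined the gain ranges from about 2 points (r=.8) to 15 points (r=.5), and ANCOVA was ahead in every one. Whether RM-ANOVA falls below 80% depends on the number analysed and the threshold applied. The change should be made, but the planned test would not give a wrong answer.

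**What to change.** In Section 14.0, Hypothesis 2, make the primary test a linear model of the T2 role-play score on arm with the T1 role-play score as a prespecified covariate, included whether or not the arms differ at baseline. Report the adjusted mean difference with its confidence interval. Fit the model within the multiple imputation already planned for missing data. RM-ANOVA can stay as a sensitivity analysis. Restate the H2 power for this model, giving the number per arm and the loss assumed.

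This costs one sentence of analysis text and a revised power line. It needs no further participants, visits or measurements, and it matches the ANCOVA already written for H4. It should be settled before outcome data are analysed by arm.

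### The second Hypothesis 2 power statement (160 subjects, 4.7% reduction, d = .32, 80% power) matches an unadjusted 0.05 level; at the plan's 0.0125 level power is 61% for 4.7% and 54% for d = .32

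*Combined protocol and SAP*

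**What the plan says.** All of this is in Section 14.0, Data Analysis Plan for Aims 1 & 2.

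- **Level.** Under Hypothesis 1 the plan sets a "two-sided 0.05/4=.0125 level test" and adds that "our power analysis is conservative, relying on Bonferroni corrections for all tests".
- **Hypothesis 2 inputs.** The test is a two-time-point RM-ANOVA. The plan says "we expect r=.7 between T1 and T2 scores" and "our best power estimate assumes a medium effect size contrasting IPS Only with IPS+VR (d=.67-.25=.42"), which it converts to a 6.9% reduction in within-subject error.
- **First power statement.** "Thus, 80 subjects at .0125 level will yield 82% power to detect this effect".
- **Second power statement.** "For the ANOVA model, 160 subjects will be sufficient to detect a reduction of within subject error of 4.7% with 80% power". The plan then equates this to d = .62 in IPS+VR against d = .30 in IPS Only, "a difference of d=.32". No significance level is given.

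The power statements for Hypotheses 3 and 4 both name the 0.0125 level.

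**The concern.** The two Hypothesis 2 statements cannot both hold at one sample size and one level: power of 82% for a 6.9% reduction cannot still be 80% for a 4.7% reduction. Sample size does not explain the gap, because the first statement already needs all 160 subjects. The level is what remains. A reader will apply 0.0125 to the second statement, since the sentence before it and the all-tests statement both say so.

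What is at stake is the claimed sensitivity of Hypothesis 2, one of the hypotheses carrying the adjusted level. If the trial finds no difference in interview skills, the plan as written lets a reader conclude that an effect of d = .32 would probably have been found. At 0.0125 the chance of finding it is 54%.

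**Working it through.** **Inputs, all from Section 14.0.** N = 160 (80 per arm); pre-post correlation r = .7; two-sided level 0.0125; effects d = .42, 4.7% and d = .32.

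**Method.** With two time points, the treatment-by-time F test is the two-sample test on change scores.

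- SD of change = √(2(1 − r)) = √0.6 = 0.775
- f = d / (2 × 0.775)
- Error reduction = f² / (1 + f²)
- Power from the noncentral F with 1 and N − 2 = 158 df and noncentrality N × f²

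**Step 1: reproduce the first statement (d = .42).** f² = (0.42/1.549)² = 0.0735. Error reduction = 0.0735/1.0735 = 6.85% (stated 6.9%). Noncentrality = 160 × 0.0735 = 11.76. Power at 0.0125 = 81.5% (stated 82%). With 80 subjects in total, power would be 45%, so the stated 80 must mean per arm. The method, r, N and level are therefore the plan's own.

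**Step 2: the 4.7% reduction.** f² = 0.047/0.953 = 0.0493. Noncentrality = 160 × 0.0493 = 7.89. Power is 61.2% at 0.0125 and 79.7% at 0.05. The level that gives exactly 80% is 0.051.

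**Step 3: the conversion to d.** A 4.7% reduction is d = 2 × √0.0493 × 0.775 = .344. For d = .32, f² = (0.32/1.549)² = 0.0427, the error reduction is 0.0427/1.0427 = 4.1%, and noncentrality is 160 × 0.0427 = 6.83. Power is 53.6% at 0.0125 and 73.8% at 0.05. On change scores, 80% for d = .32 holds at neither level.

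**Step 4: what 160 subjects can detect with 80% power.**

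| Two-sided level | Error reduction | d |
|---|---|---|
| 0.05 | 4.73% | .345 |
| 0.0125 | 6.64% | .413 |

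The stated 4.7% is the 0.05 row. The stated .32 falls short of .413 by (.413 − .32)/.413, about 23%. At 0.0125, 80% power would need about 230 subjects for 4.7% and about 265 for d = .32.

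**Step 5: variants.**

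| Variant | Power for 4.7% | Power for d = .32 |
|---|---|---|
| Level 0.05/3, N = 160 | 65% | 58% |
| One-sided 0.0125, N = 160 | 71% | 64% |
| 0.0125, N = 144 (10% missing, which the plan states for Hypothesis 1 only) | 56% | 48% |
| 0.0125, N = 180 (the recruitment figure in Section 3.0) | 68% | 60% |

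With an ANCOVA residual SD of √(1 − 0.49) = 0.714, d = .32 corresponds to 4.8%, with 80% power at 0.05 and 62% at 0.0125. That SD would turn d = .42 into 8.0%, not the stated 6.9%, so it is not the conversion used in the first statement.

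**The case against.** The strongest reply is that Bonferroni is not the planned test. The plan says "we will adjust the 3 primary tests using a false discovery rate at 0.05", and a step-up procedure can judge Hypothesis 2 at anything up to 0.05. If that procedure is Benjamini-Hochberg, the tests are independent, and each of the other primary effects has 80% power at 0.0125 (all three are assumptions), simulation gives about 79% power for 4.7% and 73% for d = .32. If the other effects are null, power falls back close to the Bonferroni figures. So 61% and 54% are the power at the stated planning level, and roughly a floor for the final procedure. This stands as a limit on how the figures are read. It does not rescue the sentence, because the plan presents its power figures as Bonferroni-based and conservative, and this one is not.

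Four further points are fair:

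- The sentence never states 0.05. That level is inferred from the close match of 4.73% to 4.7%. The demonstrable fault is an unstated level that is inconsistent with its neighbours.
- The plan counts both three and four primary tests, so 0.0125 is itself not settled. At 0.05/3 the claim still fails.
- The document does not show how it reached d = .32, and the gap from .34 is small.
- The second statement is a secondary sensitivity claim. Neither the sample size nor the choice of analysis depends on it.

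**Conclusion.** The point holds. On the inputs that reproduce the plan's first Hypothesis 2 figure, the second figure is right only near an unadjusted 0.05. At 0.0125, power is 61% for a 4.7% reduction and 54% for d = .32, against a stated 80%, and the two effect sizes do not match each other. The smallest difference detectable with 80% power is d = .41 (6.6%).

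This assumes 160 analysed subjects in equal arms, r = .7 and the RM-ANOVA the plan specifies. With 144 analysed the detectable d is .44, and with 180 it is .39. The plan's best estimate, 82% power for d = .42, is sound, so the error lies in the claimed sensitivity and not in the trial's size. It should be corrected.

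**What to change.** Replace the second Hypothesis 2 power statement and its conversion with text to this effect: with 160 analysed subjects (80 per arm), r = .7 and a two-sided 0.0125 level, the RM-ANOVA has 80% power for a between-arm difference in change of d = .41, a 6.6% reduction in within-subject error; power for d = .32 is 54%. In the sentence before, write 80 per arm for 80 subjects. When the plan settles on three or four primary tests, recompute if the level changes.

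The cost is two sentences of text and a less favourable detectable effect. No extra data are needed.

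A separate improvement, not needed to correct the arithmetic, is to test Hypothesis 2 by ANCOVA of the T2 role-play score on arm and T1 score. At r = .7 this raises power for d = .42 from 82% to 88% and lowers the detectable difference at 0.0125 from .41 to .38. It uses a baseline score already collected, and the plan already names ANCOVA under Hypothesis 4. The gain depends on the assumed correlation, and the change should be fixed before outcome data are examined by arm.
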